1.0 PROTOCOL SUMMARY AND/OR SCHEMA

Inhibition of $BRAF^{V600E}$ kinase has emerged as effective therapeutic strategy for patients with metastatic melanoma harboring a $BRAF^{V600E}$ mutation. It is reasonable to speculate that $BRAF^{V600E}$ kinase inhibitors will benefit molecularly selected melanoma patients at earlier stages of the disease. Patients with stage IIIC melanoma are at an extremely high risk of disease recurrence and death despite definitive surgical resection. Data from our Center indicate that the relapse-free survival (RFS) for stage IIIC disease is only 24% at 2 years. In this single center phase II trial, patients with surgically-resected stage IIIC melanoma characterized by a $BRAF^{V600E}$ or $BRAF^{V600K}$ mutation will be treated with 4 cycles of adjuvant dabrafenib and monitored clinically and radiographically for disease recurrence for 24 months following surgical resection. We will test the hypothesis that adjuvant $BRAF$ kinase inhibition will improve RFS from 24% to 51% at 24 months. The planned accrual is for 23 patients. The primary objective of the study will be to determine the RFS at 24 months. The trial would be considered positive if 9 or more patients are relapse-free and alive at 24 months. The trial would be terminated early if at any time 15 patients relapsed or died before 24 months. Secondary objectives include the assessment of dabrafenib toxicity and the determination of overall survival (OS). In an exploratory fashion, pretreatment tumors biopsies and biopsies at the time of relapse will be obtained to characterize the tumors genetically and to assess for mechanisms of resistance to $BRAF$ inhibition. Serial blood samples will also be obtained and used to determine if circulating tumor-derived exosomes can predict melanoma recurrence.

STUDY SCHEMA

2.0 OBJECTIVES AND SCIENTIFIC AIMS

2.1 Primary Objective

To determine the RFS at 24 months for patients with Stage IIIC melanoma harboring a *BRAF*^{V600E/K} mutation who are treated with definitive surgical resection followed by four cycles of adjuvant dabrafenib administration.

2.2 Secondary Objectives

To determine overall survival.

To assess toxicity.

2.3 Exploratory Objectives

To characterize the genetic heterogeneity of *BRAF*-mutated melanomas and explore mechanisms of intrinsic and acquired resistance to dabrafenib.

To evaluate the ability of circulating tumor-derived exosomes to predict melanoma recurrence.

3.0 BACKGROUND AND RATIONALE

3.1 Regional metastatic melanoma

It is projected that there will be 76,250 new cases of cutaneous melanoma in the United States in 2012 [1]. Ten to 13% of patients with cutaneous melanoma will present with regional metastatic disease. Regional metastatic melanoma [American Joint Commission on Cancer (AJCC) Stage III disease] is defined by the neoplastic involvement of the regional lymph nodes and/or regional cutaneous disease in-transit. Independent prognostic factors for this stage of disease include the depth of the primary tumor, the presence of ulceration in the primary tumor, the number of tumor-bearing lymph nodes, and the burden of nodal disease [2]. Stages III patients are sub-classified into three groups (i.e. IIIA, IIIB and IIIC) by presence or absence of these important prognostic factors.

Definitive surgical resection is the only widely accepted modality for long-term disease control and cure. Even in the setting of a complete surgical resection, the risk of disease recurrence and death is extremely high, particularly for patients with stage IIIC disease. Data from our Center show that the 5-year relapse-free survival for stage IIIC melanoma is 15%; the 5-year overall survival is only 11% [3]. This indicates that relapse is almost equivalent to death in patients with stage IIIC melanoma. Preventing disease relapse is thus a key objective.

Patients with surgically resectable stage IIIC melanoma have few tolerable and effective systemic therapies available to alter the natural history of their disease. Adjuvant high dose and pegylated interferon therapy have been shown to offer a modest relapse-free survival benefit in randomized studies [4, 5]. Unfortunately, interferon-based adjuvant therapy is poorly tolerated and no study has demonstrated an overall survival advantage [4-7]. As such interferon is not uniformly accepted as a standard of care, despite being the only FDA approved agent for use in the adjuvant setting. Clinical trials of adjuvant immunotherapies,

vaccines and chemotherapies have also been disappointing and have not modified the risk of recurrence or death from melanoma after definitive surgical resection [8].

As surgically resectable stage IIIc melanoma has a high mortality with minimal effective treatments, novel adjuvant and neoadjuvant therapies are clearly necessary to improve patient outcomes.

3.2 Mutations in *BRAF* activate the MAPK pathway in melanoma

A subset of melanoma is driven by constitutive activation of the mitogen-activated protein kinase (MAPK) signaling cascade [9]. Fifty to sixty percent of melanomas harbor activating mutations in *BRAF*. Ninety percent of these mutations occur at codon 600 [10]. The most common mutation at this position is a missense error resulting in a valine to glutamate substitution (i.e. *BRAF*^{V600E}). Other variants have also been observed and include *V600K*, *V600R* and *V600D* [11]. It is now well-established that melanomas with *BRAF*^{V600} mutations are dependent on signaling through the MAPK pathway for cellular proliferation and survival [12] and that blocking signaling through this pathway results in cell cycle arrest and apoptosis *in vitro* and *in vivo* [13]. These preclinical observations have led to the clinical development of two potent inhibitors of mutated-*BRAF* kinase: vemurafenib and dabrafenib.

3.3 Vemurafenib and Dabrafenib

In vitro studies indicate that vemurafenib and dabrafenib effectively block signaling through the MAPK pathway by inhibiting *BRAF*^{V600E} kinase activity [14, 15]. The IC₅₀ of vemurafenib for *BRAF*^{V600E} kinase is 31nM [14]. Dabrafenib is a more potent inhibitor of this kinase *in vitro* with a corresponding IC₅₀ of 0.7nM [15]. Dabrafenib also effectively inhibits *BRAF*^{V600K} and *BRAF*^{V600D} kinase with an IC₅₀ of 0.5 and 1.8nM, respectively. Both vemurafenib and dabrafenib induce growth suppression, rapid cell cycle arrest, and apoptosis in melanoma cell lines characterized by a *BRAF*^{V600E} mutation [15, 16]. Likewise, administration of each of the agents *in vivo* results in profound tumor regression in murine xenograft melanoma models [14, 15].

The completed phase I, II and III clinical trials of vemurafenib have confirmed that this agent is a safe and effective treatment modality for patients with metastatic melanoma [17-19]. The pivotal, randomized, open label, phase III trial (BRIM 3) comparing vemurafenib with dacarbazine in patients with previously untreated, *BRAF*-mutated metastatic melanoma led to FDA licencing of the agent in August of 2012 [18]. Forty-eight percent of patients treated with vemurafenib had a confirmed objective response (2 CR and 104 PR) by RECIST criteria. The median time to response was 1.5 months. At the time of first interim analysis, the median follow-up for patients treated with vemurafenib and dacarbazine was 3.8 months and 2.3 months, respectively. Importantly, vemurafenib was associated with a statistically significant relative risk reduction of 63% in the risk of death and of 74% in the risk of death or progression of disease when compared to dacarbazine. These beneficial effects on outcome

were independent of disease stage [i.e. unresectable stage IIIC, Stage IV (M1a, M1b and M1c)]. In the phase II trial of vemurafenib, nearly 90% of patients achieved a maximal response by 4 months [19].

The safety and clinically efficacy of dabrafenib appears to be equivalent to vemurafenib. A multicenter phase VII trial assessed the tolerability and activity of dabrafenib in patients with previously-treated *BRAF*-mutated metastatic melanoma and other solid tumor [20]. Although a maximum tolerated dose was not identified, dabrafenib at 150 mg twice a day was ultimately selected as the recommended phase II dose. This schedule was comparable in antitumor activity, pharmacokinetic properties and pharmacodynamic effect to higher doses. Twenty-five of 36 (69%) *BRAF*-mutant metastatic melanoma patients who were treated with the recommend phase II achieved an unconfirmed partial or complete response. The median duration of response was 6.2 months; the median progression-free survival was 5.5 months. Tumor biopsies were obtained prior to treatment and 7 (\pm 4) days into treatment in 12 patients. Importantly, a marked decrease in proliferation with associated necrosis and apoptosis was observed in all samples. Two phase II studies of dabrafenib have since confirmed its antitumor activity in melanoma [21, 22]. Response rates in these studies range from 31% to 58% and thus appear to be equivalent to those observed with vemurafenib, which range from 48 to 57% [17-19].

In a multicenter, open label, randomized phase III clinical trial (BREAK-3) in patients with unresectable stage IIIC or IV *BRAF*-mutated melanoma dabrafenib was found to improve progression-free survival compared dacarbazine [23]. Median progression-free survival was 6.7 months for dabrafenib as compared to 2.9 months with dacarbazine with a hazard ratio for progression of 0.35. These data are equivalent to the data obtained from BRIM-3, the randomized phase III study comparing vemurafenib to dacarbazine in patients with unresectable stage IIIC or IV *BRAF*-mutated melanoma. In BRIM-3, the PFS for patients receiving vemurafenib was 6.9 months versus 1.6 months for dacarbazine (HR 0.38) [18, 24].

3.4 Studyrationale

Preclinical *in vitro* and *in vivo* data with both vemurafenib and dabrafenib indicate that inhibitors of mutated-*BRAF* kinase induce cell death in melanoma cells harboring a *BRAF* mutation [14, 16]. Clinical data demonstrate that inhibition of mutated-*BRAF* kinase results in rapid and significant tumor shrinkage in more than 50% of patients with advanced melanoma characterized by *BRAF*^{V600} mutations independent of disease stage [15, 17-19]. Correlative studies show that apoptosis and tumor necrosis are apparent within one week after the initiation of *BRAF* kinase inhibitors. Anecdotally, we have observed several pathologic complete responses following metastasectomy after best response to *BRAF* kinase inhibition. This indicates that inhibitors of mutated-*BRAF* kinase have the ability to eradicate bulky metastatic disease. It is thus reasonable to speculate that inhibition of mutated-*BRAF* kinase will benefit molecularly selected melanoma patients at earlier stages of the disease.

The underlying hypothesis of this trial is that treatment of micrometastatic disease for 4 cycles will be sufficient to improve RFS in stage IIIC patients with *BRAF* mutations who are currently free of disease. Based on our data at MSKCC [3], stage IIIC patients would be expected to have a RFS of only 24% at 24 months. We will test the hypothesis that 4 cycles of adjuvant dabrafenib will result in an improvement in RFS from 24% to 51% at 24 months.

The duration of treatment (i.e. 4 cycles) was based on the time to maximal response in patients with bulky disease treated with BRAF inhibitor as well as the observation that resistance to these agents generally develops after month six. It was also felt that if continuous adjuvant treatment with dabrafenib were necessary to improve relapse-free survival, then treatment at relapse would likely be just as effective and the rationale for adjuvant therapy would be undercut.

3.5 Correlative studies

Resistance to BRAF kinase inhibition

Despite the major success of *BRAF* inhibition, subsets of melanomas are intrinsically resistant to inhibitors of mutated *BRAF* kinase [25]. Fourteen percent of melanoma patients had primary progressive disease on the phase II trial of vemurafenib [19]. Genetic heterogeneity may in part explain *de novo* resistance. Mutations in other signaling pathways and/or tumor suppressor genes may abrogate the cellular dependence on mutated-*BRAF* activity. To this end, concomitant mutational inactivation of *PTEN* and *RB1* has been observed in *BRAF* mutated cell lines and these co-mutations render these cell lines resistant to *BRAF* kinase inhibition [26, 27].

Melanomas also appear to develop acquired resistance to *BRAF* inhibition. The median progression-free survival to vemurafenib is 5-7 months in the metastatic setting [18]; the progression-free survival to dabrafenib appears to be similar. Investigators have proposed numerous candidate mechanisms for acquired resistance [28-32], however, reactivation of the RAS-RAF-MEK-ERK pathway appears to be a prominent mode of resistance to *BRAF* kinase inhibition. Acquired *N-RAS* (Q61K) and *MEK* (C121S) mutations [30-32] as well as a unique splice variant of *BRAF*^{V600E} [32] have been shown to up-regulate the MAPK signaling pathway and convey resistance to *BRAF* kinase inhibition.

Additional mechanisms will likely be postulated in the months to come. Unfortunately, few patient samples have actually been interrogated to date. The proposed trial is uniquely positioned to acquire substantial tumor tissue. Tumors obtained prior to treatment will be genetically characterized by whole exome sequencing to identify co-mutations in *BRAF* mutated melanomas. Tumor will also be obtained in virtually all patients at time of progression since tissue confirmation of progression is a standard of care. Tumor biopsies at progression will allow discovery of resistance mechanisms in a prospective manner.

Circulating tumor-derived exosomes as a marker of melanoma recurrence

Exosomes are microvesicles derived from the luminal membrane of the endocytic compartment in both normal and neoplastic cells [33]. These membrane-bound particles range between 30 and 100 nanometers in size and are constitutively released into the extracellular matrix after fusion of endosome with the cell membrane. Exosomes contain a number of subcellular elements including messenger RNAs, micro-RNAs, DNA, and a variety of proteins involved in multiple cellular processes such as antigen presentation, cell targeting and adhesion, apoptosis, signal transduction, and cell proliferation. Thus, exosomes play a critical role in mediating intercellular communication allowing for the horizontal transfer of information between cells [34].

Peinado and colleagues [34] recently isolated and characterized exosomes from the sera of patients with increasing stages of cutaneous melanoma. Exosome size distribution and absolute number did not differ based on clinical stage. Interestingly, exosomes isolated from patients with advanced stages of melanoma were qualitatively different from normal controls as well as individuals with earlier stages of the disease. Specifically, exosomes from patients with Stage IV disease were characterized by both higher concentrations of proteins and a unique protein signature including tyrosinase-related protein-2 (TYRP2), very late antigen 4 (VLA-4), heat shock protein 70 (HSP70), and the MET oncoprotein. Exosomal levels of TYRP2 were also significantly higher in patients with Stage III disease and in a retrospective analysis of 29 patients correlated with disease progression. In an exploratory fashion, we will obtain serial peripheral blood samples from all patients on this trial to measure and characterize tumor-derived exosomes in patients with surgically resected stage IIIC disease. We will prospectively test the hypothesis that qualitative changes in circulating exosomes will be able to predict melanoma recurrence.

4.0 OVERVIEW OF STUDY DESIGN/INTERVENTION

4.1 Design

This is a single institution, single arm, phase II trial of adjuvant dabrafenib in patients with surgically-resected stage IIIC cutaneous melanoma characterized by a *BRAF*^{V600E/K} mutation.

4.2 Intervention

Following definitive surgical resection, eligible patients will receive dabrafenib at 150 mg twice a day by mouth for 4 cycles. One cycle is 28 days.

5.0 THERAPEUTIC/DIAGNOSTIC AGENTS

5.1 Mechanism of Action

Dabrafenib, a 4-(3-aminosulfonylphenyl)-5-(pyrimidin-3-yl) thiazole, is an orally bioavailable, small molecule, ATP-competitive inhibitor of *BRAF*^{V600} kinase. Dabrafenib (IND # 105032) is an investigational agent manufactured and supplied by Novartis Pharmaceuticals. Detailed information regarding the pharmacologic properties of dabrafenib can be found in the Investigator's Brochure.

5.2 Formulation, Storage and Packaging

Dabrafenib will be provided as 50 mg and 75 mg capsules. Each capsule contains 50 mg or 75 mg as free base present as the mesylate salt. The inactive ingredients include microcrystalline cellulose, magnesium stearate, gelatin, FDA red iron oxide and titanium dioxide. The drug should be stored in a dry location at room temperature not exceeding 25°C.

5.3 Administration of Dabrafenib

Dabrafenib will be dosed at 150 mg twice a day by mouth. Patients are instructed to take 150 mg in the morning and 150 mg in the evening, approximately 12 hours apart. Dabrafenib should be administered under fasting conditions, either 1 hour before or 2 hours after a meal. If a study participant vomits after a dose, the patient should be instructed not to retake the dose and should take the next dose at its scheduled time. If a dose is missed, it can be taken up to 6 hours prior to the next dose to maintain the twice daily regimen. Instructions for dose modifications can be found in Section 9.

6.0 CRITERIA FOR SUBJECT ELIGIBILITY

6.1 Subject Inclusion Criteria

- 6.1.1 AJCC (2009) stage IIIC cutaneous melanoma rendered free of disease by surgical resection no greater than 90 days prior study enrollment. Patients with unknown primaries will be eligible for this trial. Patients with a history of resected stage I or II cutaneous melanoma who subsequently have their first disease recurrence meeting the criteria for stage IIIC disease will also be eligible for this trial.
- 6.1.2 Patients must have clear margins after wide local excision. Patients with nodes that are palpable or detectable on radiologic imaging must have an adequate lymphadenectomy.
- 6.1.3 Patients must be adequately recovered from surgery, radiation therapy, or any surgical complications prior to enrollment. In general, this means patients will be off antibiotics from wound infections and drains removed. However, if necessary, patients can be treated with a drain in place at the discretion of the PI if the 90 days window is about to expire.
- 6.1.4 Histologic proof of melanoma reviewed and confirmed by MSKCC.
- 6.1.5 A documented *BRAF*^{V600E} or *BRAF*^{V600K} mutation by genotyping or IHC [35] performed by a CLIA certified laboratory.
- 6.1.6 Age \geq 16 years old.
- 6.1.7 ECOG performance status = 0 or Karnofsky Performance Status equivalent (Appendix A).
- 6.1.8 The ability to swallow pills.
- 6.1.9 Patients must have adequate organ and marrow function as defined below:

Absolute neutrophil count	≥ 1.5 K/mcL
Platelets	≥ 100 K/mcL
Hemoglobin	≥ 9.0 g/dL
Total bilirubin	≤ 1.5 X institutional upper limit of normal (ULN) ≤ 3.0 X institutional ULN if the patient has Gilbert's Syndrome
AST (SGOT) and ALT (SGPT)	≤ 2.5 X institutional ULN
Creatinine	≤ 1.5 X institutional ULN or creatinine clearance (calculated or measured) > 60 ml/min

6.1.10 Women with child bearing potential and men with reproductive potential must be willing to practice acceptable methods of contraception.

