9.3.2 Cautionary Medications

The following medications should be used with caution (see Appendix B):

- Drugs that are mild/moderate inhibitors or inducers of CYP3A, CYP2C8, PGP or BCRP because they may alter dabrafenib concentrations.

- *In vitro* dabrafenib inhibits CYP2C8, CYP2C9, and CYP2C19 activity. Concentration of medications metabolized by these enzymes may be altered by dabrafenib.
- *In vitro* dabrafenib induces CYP3A4, CYP2B6, CYP2C8, CYP2C9, and CYP2C19. Co-administration of dabrafenib and medications which are affected by the induction of these enzymes may result in loss of efficacy. If co-administration of these medications is necessary, investigators should monitor subjects for loss of efficacy or consider substitutions of these medications.

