11.9 Reproductive Risk

Preclinical data indicate that dabrafenib is detrimental to the developing fetus. Thus, fertile patients must not become pregnant or father a child while on study. Contraception should be utilized for the duration of the study and for at least 6 months after study completion. Women should not breastfeed while on study.

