APPENDIX B: Prohibited and Cautionary Medications

PROHIBITED MEDICATIONS	
Strong CYP2C8/3A/PGP/BCRP1 Inhibitor/Inducer. May alter levels of DABRAFENIB	Therapeutic Area
Clarithromycin, telithromycin, rifamycin class agents (e.g. rifampin, rifabutin, rifapentine), toleandomycin	Antibiotics
Itracozazole, ketoconazole, posaconazole, voriconazole	Antifungals
Nefazodone	Antidepressants
Gemfibrozil	Hyperlipidemia
Carbamazepine, phenobarbital, amiodarone, phenytoin, s-mephenytoin, bosentan, mibefradil, conivaptan	Miscellaneous
Cyclosporine	Immunosuppressive agents

CAUTIONARY MEDICATIONS	
CYP2C8/C9/C19 Substrates; these drugs may be altered (increased or decreased) by DABRAFENIB	Therapeutic Area
Cerivastatin	HMG-CoA Reductase Inhibitors
Tolbutamide, nateglinide, repaglinide	Antidiabetics
Amitriptyline, clomipramine, imipramine	Antidepressants
Mild/Moderate Inhibitor of CYP3A, CYP2C8, PGP and BCRP1; These drugs may increase concentrations of DABRAFENIB	
	Therapeutic Area
Erythromycin	Antibiotic
Fluconazole	Antifungal

Diltiazem, verapamil	Antiarrhythmics
Aprepitant, cimetidine, montelukast	Miscellaneous
Substrates of CYP3A4/CYP2B6/CYP2C8/CYP2C9/CYP2C19 that may be affected by induction by DABRAFENIB; These drugs may lose efficacy when co-administered with DABRAFENIB	
Therapeutic Area	
Chloramphenicol, doxycycline, erythromycin, moxifloxacin	Antibiotics
Caspofungin, fluconazole, terbinafine	Antifungals
Amlodipine, diltiazem, felodipine, nifedipine, nilvadipine, nisoldipine, verapamil	Antihypertensives
Aripiprazole, bupropion, buspirone, desipramine, haloperidol, mirtazapine, pimozide, quetiapine, trazodone	Antidepressants and Antipsychotics
Glyburide, saxagliptin, tolbutamide	Antidiabetics
Lamotrigine, valproate, divalproex, zonisamide,	Anticonvulsants
Alfentanil, buprenorphine, celecoxib, codeine, fentanyl, methadone, oxycodone	Analgesics
Aprepitant, cisapride, darifenacin, disopyramide, leflunomide, methohexital, oral contraceptives, quinine, ranitidine, sulfenacin, sulfasalazine, tramadol, tolvaptan	Miscellaneous
Alprazolam, brotizolam, diazepam, estazolam, midazolam, triazolam, zolpidem, zopiclone	Hypnotics and Sedatives
Diergotamine, ergotamine, eletriptan	Antimigraine agents
Everolimus, sirolimus, tacrolimus	Immunosuppressive agents
Astemizole, chlorpheniramine, ebastine	Antihistamine
Oral budesonide, methylprednisolone	Corticosteroids
Sildenafil, tadalafil, vardenafil	Erectile Dysfunction agents
Eplerenone	Selective Aldosterone Blockers

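### The contraception requirement does not mention that Appendix B lists oral contraceptives as possibly losing efficacy with dabrafenib, and the general rule for such drugs can be met by monitoring alone

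*Combined protocol and SAP*

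**What the plan says.** Four parts of the combined protocol and SAP bear on this point.

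- **6.1.10 (inclusion):** "Women with child bearing potential and men with reproductive potential must be willing to practice acceptable methods of contraception". The section does not define which methods are acceptable and cites no other section.
- **11.9 (Reproductive Risk):** "Preclinical data indicate that dabrafenib is detrimental to the developing fetus", so "fertile patients must not become pregnant or father a child while on study". On contraception it gives only a duration: "Contraception should be utilized for the duration of the study and for at least 6 months after study completion". It names no method and does not cite 9.3.2 or Appendix B.
- **9.3.2 (Cautionary Medications):** this section cites Appendix B and reports that, in vitro, "dabrafenib induces CYP3A4, CYP2B6, CYP2C8, CYP2C9, and CYP2C19". For drugs affected by that induction the instruction is: "If co-administration of these medications is necessary, investigators should monitor subjects for loss of efficacy or consider substitutions of these medications".
- **Appendix B:** under the cautionary heading for induced substrates, which warns that "These drugs may lose efficacy when co-administered with DABRAFENIB", the Miscellaneous row includes "methohexital, oral contraceptives, quinine, ranitidine".

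The exclusion criterion that cites Appendix B, 6.2.4, covers prohibited drugs only. Oral contraceptives are on the cautionary list, so 6.2.4 does not reach them.

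**The concern.** The protocol states both halves of a hazard and does not join them. One section says that the drug may harm a fetus and that pregnancy must not occur. An appendix says that the drug may weaken a common method of preventing pregnancy. A member of staff who checks eligibility against 6.1.10, or counsels a patient from 11.9, is not directed to the appendix.

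The general instruction for interacting drugs also fits contraception badly. Watching for loss of effect is sensible for a medicine whose effect can be measured and corrected, such as an antihypertensive. With a contraceptive, the visible sign of lost effect is the outcome that 11.9 forbids.

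What is at stake is fetal exposure to a drug that the protocol itself describes as harmful. The trial's statistical conclusions are not at stake.

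**Working it through.** No plan figure needs reproducing; the check is a reading of the sections against each other, with one line of arithmetic for the period concerned.

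**1. Is the population present?** Yes. Both sexes are eligible (6.3), entry is from age 16 (6.1.6), and 6.1.10 and 8.4 both provide for women of child-bearing potential.

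**2. Does any visible eligibility text exclude the pill as sole method?** No. 6.1.10 leaves acceptable methods undefined, 6.2.4 reaches prohibited drugs only, and 11.9 gives a duration without a method.

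**3. Does 9.3.2 exclude it?** It advises caution, and where co-administration is necessary it offers two options joined by *or*.

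| Option in 9.3.2 | Effect for a woman relying on the pill alone |
|---|---|
| Monitor for loss of efficacy | No protection: the loss is seen only once she is pregnant |
| Consider substitution | Protects if a substitution is made, but the wording asks only that it be considered |

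The rule can therefore be followed to the letter by taking the first option, and she remains unprotected.

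**4. Do the pregnancy tests close the gap?** No. The serum test before treatment (8.4) and the serum beta-HCG, where applicable, with the laboratory evaluations (Table 8, footnote c) detect a pregnancy. They can limit the length of an exposure but cannot prevent conception.

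**5. Over what period does the interaction matter?** Inputs from 4.2: 4 cycles of 28 days each.

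- Planned dosing: 4 x 28 = 112 days, longer if doses are held.
- Washout of the induction effect after the last dose: not given in the documents. For illustration only, assumed values of 0, 14 and 28 days give 112, 126 and 140 days.

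**6. Whom does it concern?** Female participants only. A male participant's partner does not take dabrafenib, so the co-administration warning does not apply to her contraception.

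**7. How many patients?** The documents give no information on contraceptive use, so neither the number of women affected among 23 nor a pregnancy risk can be estimated.

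**The case against.** The strongest reply is that the protocol already covers this. Appendix B names oral contraceptives. Section 9.3.2 points to that appendix, urges caution, treats co-administration as something for cases of need, and offers substitution. Section 11.9 sets an absolute outcome and 6.1.10 demands acceptable methods. A careful investigator who reads these together has good grounds to reject the pill alone, and in a single-institution trial one team applies one document. The induction evidence is in vitro, pregnancy tests are a partial safeguard, and documents not available here may specify methods.

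Much of this stands. It means the hazard is disclosed and the remaining gap is narrow. It does not remove the gap, because the protection depends on an investigator making a connection that the text does not make, and one of the two permitted options does not work for contraceptives.

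Three stronger readings are tempting, and the documents support none of them:

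- *The protocol endorses the pill alone.* It does not. It is silent in 6.1.10 and 11.9, and cautionary elsewhere. It fails to rule the pill out.
- *Women in this trial are unprotected in practice.* That cannot be known without the consent form, the eligibility checklist (15.1) and the Investigator's Brochure (5.1).
- *The size of the problem can be expressed as dosing time divided by the whole contraception period in 11.9.* Such a fraction measures no risk. Its denominator is also not fixed, since active follow-up ends at 24 months from surgery or at recurrence (10.1), and chart review continues after 24 months.

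**Conclusion.** The point holds as a patient-safety clarification. On the visible text, a woman of child-bearing potential could rely on oral contraceptives alone throughout dosing, and the investigator could comply fully with 9.3.2, although the same protocol warns that the method may lose efficacy and that the drug may harm a fetus.

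The planned period is 112 days plus an unstated washout. The number affected is unknown and may be none. Confidence is high for the wording of the protocol and does not extend to what patients are told through documents not seen here. The conclusion assumes nothing about the clinical size of the interaction; it rests only on the protocol's own decision to list oral contraceptives. The primary endpoint, decision rule, error rates and sample size are unaffected.

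**What to change.** Add one sentence to 11.9, citing 9.3.2 and Appendix B, and a cross-reference to it from 6.1.10. Suggested content: *For female participants of child-bearing potential, oral contraceptives alone do not meet the contraception requirement during dabrafenib dosing and for a washout of [sponsor to specify] after the last dose; an effective method not subject to this interaction must be added or substituted, and monitoring for loss of efficacy under 9.3.2 is not sufficient for contraceptives.*

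Leave the overall contraception duration in 11.9 as it is, and do not extend the restriction to partners of male participants. If the consent form or eligibility checklist already says this, the edit simply aligns the protocol with it.

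The cost is one sentence, one cross-reference and a sponsor decision on the washout. A few women may have to add or change a method during dosing and washout. There is no statistical cost.
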